## 11.2 DISPOSITION OF PATIENTS

Screened patients are defined as any patient who signed the informed consent.

Randomized patients consist of all patients, with signed informed consent, with a treatment kit number allocated and recorded in the IRT database, regardless of whether the treatment kit was used or not. These patients form the randomized population.

Patients treated without being randomized will not be considered as randomized and will not be included in any efficacy population.

For any patient randomized more than once, only the data associated with the first randomization will be used in any analysis population. The safety experience associated with any later randomization will be assessed separately.

The safety experience of patients treated and not randomized will be reported separately, and these patients will not be in the safety population.

## 11.3 ANALYSIS POPULATIONS

### 11.3.1 Efficacy populations

Efficacy analyses will be based on the treatment group allocated by the IRT according to the randomization schedule at the Randomization Visit (as randomized), irrespective of the treatment actually received.

#### ***11.3.1.1 Intent-to-treat /modified intent-to-treat population***

Intent-to-treat (ITT) population: all randomized patients analyzed according to the treatment group allocated by randomization.

### 11.3.2 Safety population

Safety analyses will be based on the safety population, defined as all randomized patients who receive  $\geq 1$  dose of double-blind IMP (regardless of the amount of treatment administered).

Patients will be analyzed for safety according to the treatment actually received.

In addition:

- Nonrandomized but treated patients will not be part of the safety population, but their safety data will be presented separately.
- Randomized patients for whom it is unclear whether they took the study medication will be included in the safety population as randomized.
- When a patient is exposed to both sotagliflozin and placebo, the patient will be analyzed according to the treatment to which the patient was treated with the longest duration.

### **11.3.3 Patient-reported outcome analysis populations**

The patient-reported outcome (PRO) KCCQ-12 evaluation will be based on patients included in the efficacy population who have Baseline PRO assessment, at least 1 IMP administration, and at least 1 post-baseline PRO assessment.

## **11.4 STATISTICAL METHODS**

Continuous data will be summarized by treatment group using the number of observations available, mean, SD, minimum, median, and maximum.

Categorical data will be summarized by treatment group using count and percentage (%).

In general, descriptive statistics of quantitative efficacy and safety parameters (result and change from Baseline) by scheduled visits will be provided on observed cases (OC), ie, inclusion of patients having non-missing assessments at a specific visit only.

Baseline for eGFR is defined as the value assessed by the central laboratory at Randomization. For the remaining parameters, baseline is defined as the last available value before the first dose of double-blind IMP or the last available value on or before the day of Randomization for patients who were randomized but never exposed to IMP.

### **11.4.1 Extent of study treatment exposure and compliance**

The extent of study treatment exposure and compliance will be assessed and summarized by actual treatment received for the safety population.

#### ***11.4.1.1 Extent of investigational medicinal product exposure***

Duration of IMP exposure is defined as: last dose date – first dose date + 1 day, regardless of unplanned intermittent discontinuations.

The number (%) of patients randomized and exposed to double-blind IMP will be presented by specific time periods for each treatment group. The time periods of interest will be defined in the SAP.

Descriptive statistics of duration of treatment exposure (number, mean, SD, minimum, median, and maximum) and cumulative exposure in patient year will also be presented by treatment group for the safety population.

The number (%) of patients with an up-titration as well as number (%) of patients with an up-titration followed by a down-titration will be summarized.

### **11.4.1.2 Compliance**

A given administration will be considered noncompliant if the patient did not take the dose of treatment as required by the protocol. No imputation will be made for patients with missing or incomplete data.

Treatment compliance will be summarized descriptively (N, mean, SD, median, minimum, and maximum). The percentage of patients with compliance <80% will be summarized.

### **11.4.2 Analyses of efficacy endpoints**

#### **11.4.2.1 Analysis of primary efficacy endpoints**

The time to the first occurrence of CV death or HHF in patients with LVEF <50% will be analyzed by using stratified log-rank test with region (North America, Latin America, Western Europe, Eastern Europe, and rest of the world) as stratification factor. Stratified Cox proportional hazards model with region (North America, Latin America, Western Europe, Eastern Europe, and rest of the world) as stratification factor and treatment (sotagliflozin, placebo) as fixed effect factor will be used to provide the HR estimation between sotagliflozin and placebo along with its associated 2-sided 95% confidence interval (CI).

The time to the first occurrence of CV death or HHF in the total patient population will be analyzed by using stratified log-rank test with LVEF (<50%, ≥50%) and region (North America, Latin America, Western Europe, Eastern Europe, and rest of the world) as stratification factors. Stratified Cox proportional hazards model with LVEF (<50%, ≥50%) and region (North America, Latin America, Western Europe, Eastern Europe, and rest of the world) as stratification factors and treatment (sotagliflozin, placebo) as fixed effect factor will be used to provide the HR estimation between sotagliflozin and placebo along with its associated 2-sided 95% CI.

Kaplan-Meier curves of the cumulative incidence rate will be provided by treatment groups for both primary endpoints. Patients who do not experience a primary outcome event will be considered censored at their final study visit (for patients who complete the study), or date of non-CV death, or date of last contact when information on efficacy endpoints has been retrieved (for patients who discontinue the study). Underlying assumptions of the Cox proportional hazards model will be checked using graphical methods. If proportionality is not observed, further sensitivity analysis will be performed (details will be specified in the SAP).

In addition, the primary analysis will be supported by a sensitivity analysis including events from patient's Randomization up to 30 days after the last administration of IMP or up to study completion (whichever is later), but not beyond the patient's end of study date (Follow-up Visit for patient completed study or Study Closeout Visit for patient prematurely permanently discontinued study), using the same stratified log-rank test and stratified Cox proportional hazards model described above.

### *Subgroup analysis*

Subgroup analyses will be conducted for the primary endpoints with respect to LVEF (for second primary endpoint only), region, age, gender, race, ethnicity, Baseline eGFR, and Baseline BMI group. Additional subgroups and analysis details will be provided in the SAP.

#### **11.4.2.2 Analyses of secondary efficacy endpoints**

The total number (ie, including recurrent events) of CV death, HHF, or urgent HF visit will be analyzed using the Andersen-Gill approach (52), a generalization of the Cox proportional hazards model for recurrent events with treatment, LVEF, and region as factors. For standard errors in the Andersen-Gill model, a robust variance estimator will be used (53).

Secondary time to event endpoints will be analyzed using the same stratified log-rank test with LVEF (<50%, ≥50%) and region (North America, Latin America, Western Europe, Eastern Europe, and rest of the world) as stratification factors. Stratified Cox proportional hazards model with LVEF (<50%, ≥50%) and region (North America, Latin America, Western Europe, Eastern Europe, and rest of the world) as stratification factors and with treatment (sotagliflozin, placebo) as fixed effect factor will be used to provide the HR estimation between sotagliflozin and placebo along with its associated 2-sided 95% CI. The LVEF factor will not be included in the statistical model as stratification factor if the endpoint is defined in patients with LVEF <50%. Kaplan-Meier curves of the cumulative incidence rates will be provided by treatment groups.

#### **11.4.2.3 Other endpoints**

Other time to event endpoints will be analyzed using the same stratified Cox proportional hazards model described for the second primary endpoint with LVEF and region (North America, Latin America, Western Europe, Eastern Europe, and rest of the world) as stratification factors and treatment as fixed effect factor. The LVEF will not be included in the statistical model as stratification factor if the endpoint is defined in a subgroup of patients by LVEF, eg, LVEF<40%.

Number (%) of patients with at least 1 new onset of atrial fibrillation, atrial flutter, or ventricular arrhythmia since Randomization will be summarized by treatment group. For other endpoint of changes in concomitant loop diuretic medications, summary tables will be provided.

Analysis of other endpoints will be descriptive with no statistical testing. Summary statistics at scheduled visits using observed data will be provided by treatment group. Graphical presentations will also be used to illustrate trends over time if applicable.

#### **11.4.2.4 Multiplicity considerations**

[figure not shown]
The graphical approach (1) will be used to control the family-wise type 1 error rate at 0.05 levels.

In graphical approach, the testing procedure is fully determined by an initial weighted graph where the elementary hypotheses are represented by vertices with associated weights representing the local significance levels. The weight associated with a directed edge between any two vertices indicates the fraction of the (local) significance level at the initial vertex (tail) that is added to the

significance level at the terminal vertex (head) if the hypothesis at the tail is rejected. Together with the algorithm as specified by Bretz et al (1) for sequentially updating the graph after rejection of a hypothesis, this approach controls the family-wise type I error rate strongly at level  $\alpha$ .

As shown by Bretz et al., (1) the test decisions are independent of the order of rejection. If in a step of the algorithm more than one hypothesis can be rejected, the choice of the hypothesis  $H_i$  does not influence the total set of hypotheses that eventually can be rejected. The initial graph and the algorithm unequivocally define the testing strategy.

**Initial Graph:**

Note:  $\epsilon=0.001$ .

There are two primary hypotheses and six secondary hypotheses will be included in the multiple testing procedure as below:

**Primary hypotheses:**

- H1:** Time to first occurrence of CV death or HHF in patients with LVEF <50%
- H2:** Time to first occurrence of CV death or HHF in the total patient population

## Secondary Hypotheses

- H3:** Total number (ie, including recurrent events) of CV death, HHF, or urgent HF visit in total patient population
- H4:** Time to CV death in patients with LVEF <50%
- H5:** Time to all-cause mortality in patients with LVEF <50%
- H6:** Time to first occurrence of the composite of positively adjudicated sustained  $\geq 50\%$  decrease in eGFR from Baseline (for  $\geq 30$  days), chronic dialysis, renal transplant, or positively adjudicated sustained eGFR <15 mL/min/1.73 m^2 (for  $\geq 30$  days) in total patient population
- H7:** Time to CV death in total patient population
- H8:** Time to all-cause mortality in total patient population

All tests will be two-sided. Significance levels  $\alpha_1 = 0.05$

( $\alpha_2 = \alpha_3 = \alpha_4 = \alpha_5 = \alpha_6 = \alpha_7 = \alpha_8 = 0$ ) are initially defined such that they sum up to  $\alpha = 0.05$ .

The procedure is as follows: Test the hypotheses  $H_i$ ,  $i=1, 2, \dots, 8$ , each at its local significance

level  $\alpha_i$ . If a hypothesis  $H_i$  can be rejected, reallocate its level to other hypotheses according to a pre-specified rule represented by the initial weighted graph. Update the reallocation weights in the reduced graph and repeat the testing step for the remaining, non-rejected hypotheses with the updated local significance levels. This possibility leads to further rejected null hypotheses with the updated local significance levels. The procedure is repeated until no further hypothesis can be rejected.

The reallocation of the local alpha levels is fully determined by the initial graph of the multiple testing strategy.

No further multiplicity adjustments will be made for other efficacy endpoints or subgroup analyses for which nominal p-values may be provided for descriptive purpose only.

### 11.4.3 Analyses of safety data

Safety endpoints are presented in [Section 9.2](#). The summary of safety results will be presented by treatment group. All safety analyses will be performed on the safety population as defined in [Section 11.3](#) using the following common rules:

The Baseline value is generally defined as the last available value before the first dose of double-blind IMP.

The following definitions will be applied to laboratory parameters and vital signs:

- The potentially clinically significant abnormality (PCSA) values are defined as abnormal values considered medically important by the Sponsor's Global Pharmacovigilance and Epidemiology department and in effect at the time of the final SAP approval. Potentially clinically significant abnormality criteria for parameters not cited in the protocol as safety parameters will not be analyzed.
- The PCSA criteria will determine which patients had at least 1 PCSA during the on-treatment period, taking into account all evaluations performed during the on-treatment period, including unscheduled or repeated evaluations. The number of all such patients will be the numerator for the on-treatment PCSA percentage.

Please note that the same observation period will be used for all safety observations (ie, AE and death).

The "observation periods" of safety data as defined below are applicable for classification of AEs, deaths, determination of on-treatment PCSA values and the last on-treatment value for the laboratory, vital sign, and ECG parameters. The observation period of safety data will be divided into 3 segments:

- The Screening period is defined as the time from signed informed consent to Randomization.
- The on-treatment period (treatment-emergent AE [TEAE] period) is defined as the time from the first dose of double-blind IMP up to 10 days (1 day for hypoglycemia) after the last dose of double-blind IMP. The 10-day interval is chosen based on the half-life of the IMP in patients with moderate renal dysfunction.
- The post-treatment period is defined as the time starting 11 days after the last dose of double-blind IMP (after the on-treatment period).
- On-study observation period is defined as the time from randomization until the end of the study.

#### **11.4.3.1 Analysis of adverse events**

**Pre-treatment AEs** are AEs that developed or worsened or became serious during the time between date of informed consent and the first dose of double-blind IMP.

**Treatment-emergent AEs** are AEs that developed or worsened (according to the Investigator's opinion) or became serious during the on-treatment period.

**Post-treatment AEs** are AEs that developed or worsened or became serious during the post-treatment period.

The primary focus of AE reporting in the CSR will be on TEAEs. Pre- and post-treatment AEs will be described separately. Efficacy events that are waived from reporting as AEs are described in [Section 10.4.1.4](#).

## All adverse events

The number (%) of patients with at least 1 AE will be tabulated by System Organ Class (SOC) (sorted by internationally agreed order), high-level group term (HLGT), high-level term (HLT) and Preferred Term (PT) sorted in alphabetical order by treatment group. Multiple occurrences of the same event for the same patient will be counted only once in the tables within a treatment period. The denominator for computation of percentages is number of patients within each treatment arm in the safety population.

Summaries of all TEAEs in each treatment group will include:

- The overview of AEs, summarizing number (%) of patients with any:
  - Treatment-emergent AE
  - Serious TEAE
  - Treatment-emergent AE leading to death
  - Treatment-emergent AE leading to permanent treatment discontinuation
- The number (%) of patients with at least 1 TEAE by primary SOC, HLGT, HLT, and PT
- Summary of TEAEs by maximal severity (severe, moderate, mild), presented by primary SOC and PT
- Summary of TEAEs possibly related to IMP, presented by primary SOC, HLGT, HLT and PT

A detailed listing of TEAE summaries will be provided in the SAP.

## Death and serious adverse events

Deaths and treatment-emergent SAEs will be summarized and presented as number (%) of patients by treatment group.

The following deaths will be summarized by treatment received for the safety population:

- Number (%) of patients died by study period (on-study and on-treatment) and the adjudicated death reason.
- Death in nonrandomized patients or randomized but not treated patients.
- Number (%) of patients with AEs leading to death (death as an outcome on the AE e-CRF page as reported by the Investigator), by primary SOC, HLGT, HLT, and PT, sorted by internationally agreed order of SOC and alphabetic order of HLGT, HLT, and PT.
- Number (%) of patients with TEAE leading to death (death as an outcome on the AE e-CRF page as reported by the Investigator) by primary SOC, HLGT, HLT, and PT, presenting number (%) of patients sorted by internationally agreed order of SOC and alphabetic order of HLGT, HLT, and PT.

## Adverse events leading to permanent treatment discontinuation

All TEAEs leading to permanent treatment discontinuation will be summarized and presented as number (%) of patients in each treatment group.

#### **11.4.3.2 Analysis of severe hypoglycemia**

The number (%) of patients and rate in patient-year (2 types: the number of patients with events and the total number of events per 100 patient-year) of severe hypoglycemia will be summarized by treatment group respectively. Their pattern of occurrence over time will also be assessed, as appropriate.

#### **11.4.3.3 Analysis of adverse events of special interest**

Pregnancy and symptomatic overdose with IMP will be included in overall AE summaries if any are reported. An ALT increase  $\geq 3$  x ULN will be included in laboratory PCSA summary if any.

#### **11.4.3.4 Analysis of events of special interest**

The number (%) of patients with each EOSI event will be summarized by treatment group. All events reported by the Investigators on the AE forms for special interests will be listed along with the adjudication outcome (if applicable).

The incidence of each EOSI will be summarized by treatment group. The selection of PTs will be based on standardized Medical Dictionary for Regulatory Activities query (SMQ) for each corresponding item wherever possible and will be further detailed in the SAP.

The incidence of liver-related AEs will be summarized by treatment group. The selection of PTs will be based on SMQ Hepatic disorder. Time to liver-related treatment discontinuation and time to liver death may also be provided based on hepatic disorder SMQ.

#### **11.4.3.5 Analysis of laboratory variable**

The number and percentage of patients with PCSA or by the predefined categories (if no PCSA criterion is defined) at any evaluation during the on-treatment period will be summarized for each clinical laboratory test within each treatment group. The summaries will include patients in the safety population who have at least 1 laboratory test performed during the on-treatment period and, when required by the definition of the abnormality, with an available Baseline value and available laboratory normal ranges.

Descriptive statistics will be used to summarize the laboratory results and the changes from Baseline by visit and for the last on-treatment value within each treatment group. Shift tables and other tabular and graphical methods may be used to present the results for laboratory tests of interest. Listings will be provided with flags indicating the out of laboratory range values as well as the PCSA values.

##### *Liver tests*

The liver function tests, namely ALT, AST, alkaline phosphatase, and total bilirubin, are used to assess possible drug-induced liver toxicity. The proportion of patients with PCSA values at any post-baseline visit by Baseline status will be displayed by treatment group for each parameter.

The proportion of patients with PCSA values at any post-baseline visit will also be displayed by duration of exposure for each treatment group.

Time to onset of the initial ALT and AST elevation ( $>3$  x ULN) and total bilirubin elevation ( $>2$  x ULN) will be analyzed for each parameter using Kaplan-Meier estimates, using the midpoint of the time interval between the first assessment showing the elevation and the previous assessment, presented by treatment group. Consideration should be given to the impact of the spacing of scheduled tests. A graph of distribution of peak values of ALT versus peak values of total bilirubin will also be presented. Note that the ALT and total bilirubin values are presented on a logarithmic scale. The graph will be divided into 4 quadrants with a vertical line corresponding to 3 x ULN for ALT and a horizontal line corresponding to 2 x ULN for total bilirubin.

The normalization (to  $\leq 1$  x ULN or return to Baseline if Baseline  $>ULN$ ) of elevated liver function tests will be summarized by categories of elevation (3 x ULN, 5 x ULN, 10 x ULN, 20 x ULN for ALT and AST; 1.5 x ULN for alkaline phosphatase; and 1.5 x ULN and 2 x ULN for total bilirubin), with the following categories of normalization: never normalized, normalized after permanent discontinuation of study drug. Note that a patient will be counted only under the maximum elevation category.

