### **10.3.1 Temporary treatment discontinuation with investigational medicinal products**

All IMP discontinuation should initially be considered as temporary unless permanent discontinuation is mandated by the protocol (see [Section 10.3.3](#)), and the Investigator should make best effort to resume IMP treatment as early as practically possible. There is no defined limit to the duration of temporary discontinuation. This is in part due to the fact that a patient is expected to participate in the study for a period potentially lasting several years. Reinitiation of treatment with the IMP will be done under close and appropriate clinical and/or laboratory monitoring once the Investigator is satisfied that, according to his/her best medical judgment, the IMP was unlikely to be responsible for the event concerned.

Temporary treatment discontinuation may be considered by the Investigator because of suspected AEs. Lower extremity complications (such as skin ulcers, infection, osteomyelitis, and gangrene) requiring treatment should lead to temporary discontinuation of IMP.

If DKA is suspected or confirmed, study treatment should be stopped immediately and should not be re-started unless another cause for the ketoacidosis is identified and resolved.

In addition, IMP administration should be stopped in patients admitted to the hospital for major surgical procedures or due to serious illness.

If a patient who is on an ACE-i/ARB does not tolerate the combination of the ACE-i/ARB with IMP due to hypotension/volume depletion, and one of the two agents (either the ACE-i/ARB or IMP) needs to be withheld, the ACE-i/ARB should be maintained, and the IMP should be withheld (temporarily if possible).

Reinitiation of treatment with the IMP will be done under close and appropriate clinical/and or laboratory monitoring once the Investigator is satisfied that, according to his/her best medical judgment, the responsibility of the IMP in the occurrence of the concerned event was unlikely.

Temporary discontinuation of IMP due to intolerance should be followed by reinitiation of 1 tablet of IMP qd (sotagliflozin 200 mg/matching placebo). Temporary discontinuation for any other reason should be followed by reinitiation of IMP at the last dose tolerated prior to discontinuation where possible.

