### **10.3.3 List of criteria for permanent treatment discontinuation**

The patients may withdraw from treatment with the IMP if they decide to do so, at any time and irrespective of the reason, or this may be the Investigator's decision. All efforts should be made to document the reason(s) for treatment discontinuation and this should be documented in the e-CRF.

Patients who report a CV or renal endpoint as described in [Section 10.4.1.4](#) should remain on IMP until the end of the study, unless there is a safety concern.

The following reasons shall lead to permanent IMP discontinuation:

- At the patient's own request (ie, withdrawal of consent for treatment) (note that this is regardless of whether or not the patient continues in the study)
- If, in the Investigator's opinion, continuation with the administration of the study treatment would be detrimental to the patient's well-being
- Pregnancy (in female patients)
- Any code breaking requested by the Investigator
- Specific request of the Sponsor
- Patient requires dialysis or renal transplantation

- Estimated glomerular filtration  $<15 \text{ mL/min/1.73 m}^2$

**Note:** the central laboratory will alert the Investigator for eGFR values  $<15 \text{ mL/min/1.73 m}^2$ . A repeat determination should be performed within 2 weeks, and study treatment discontinued if the repeat eGFR is  $<15 \text{ mL/min/1.73 m}^2$  (unless a reversible cause is identified [eg, short-term illness or transient volume depletion], in which case an additional repeat determination can be performed after resolution of the short-term illness).

Any abnormal laboratory value or ECG parameter will be immediately rechecked for confirmation before making a decision of permanent discontinuation of the IMP for the concerned patient.

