#### **10.4.6 Guidelines for management of specific laboratory abnormalities**

Decision trees for the management of certain laboratory abnormalities by Sanofi are provided in [Appendix D](#). The study population will be enrolled with preexisting impairment of renal function; rapid change in renal function of greater than **30% as compared** with the **mean of the prior 2 study visits** should be followed up as described in [Appendix E](#).

The following laboratory abnormalities should be monitored, documented, and managed according to the related flow chart in protocol appendices:

- Neutropenia
- Thrombocytopenia
- Increase in ALT
- Increase in creatine phosphokinase suspected to be of non-cardiac origin and not related to intensive physical activity
- Acute worsening of renal function (see [Appendix E](#))

In the event that the 'general guidance for the follow-up of laboratory abnormalities by Sanofi' [Appendix D](#) requires discontinuation of IMP, temporary discontinuation should be considered unless otherwise specified (please see [Section 10.3.1](#)).

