# 1 OVERVIEW AND INVESTIGATIONAL PLAN

## 1.1 BACKGROUND

SOLOIST is a Phase 3, multicenter, randomized, double-blind, placebo-controlled, parallel group, stratified study of sotagliflozin for the treatment of patients with worsening heart failure.

After screening, patients who met all eligibility criteria were centrally randomized via in a 1:1 ratio to sotagliflozin or placebo at randomization visit. Randomization was stratified by baseline left ventricular ejection fraction (LVEF) (LVEF<50% and LVEF≥50%) and region (North America, Latin America, Western Europe, Eastern Europe, and rest of the world).

The original plan was to randomize approximately 4000 patients. However, SOLOIST enrollment was closed in March 2020 before meeting this objective.

A recent publication in the Journal of the American College of Cardiology discussed how clinical trials and programs have been disrupted by the COVID-19 pandemic. It provided the sotagliflozin program as an example where clinical trials have been prematurely terminated. Recommendations included careful consideration of statistical issues relating to potential loss of power, increased variability in data, and challenges in adjudication of events. Similarly, the FDA has issued guidance specific to COVID-19 recognizing the potential for disruption of clinical trials and identifying some of the data and statistical issues that need to be addressed by investigators and sponsors.

This plan describes statistical efficacy analyses to be conducted by an independent academic statistician and separately verified by the Lexicon statistical team. It addresses issues related to the early termination of SOLOIST. These issues have been reviewed and the recommended steps have been chosen in a blinded fashion without the use of any unblinded interim analysis.

The termination of enrollment and follow-up of SOLOIST did not allow enough time to amend the study protocol. Changes to the intended analysis plan are reflected in this document, rather than the protocol, and this plan takes precedence where there are differences between the two documents.

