***Drug-induced liver injury***

These events will be presented in the same manner as EOSI.

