***2.4.5.2 Analyses of laboratory variables***

Summary statistics of all laboratory variables (number, mean, standard deviation, median, first quartile, third quartile, minimum, and maximum) will be calculated for each visit or study assessment by treatment group during the treatment period.

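### The liver-test normalization table has no category for tests that recover on continued IMP or after a temporary stop, so it under-reports recovery and its rows need not add up

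*Protocol*

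**What the plan says.** The liver-test part of Protocol 11.4.3.5 defines normalization as a return to the upper limit of normal (ULN) or below, or to Baseline where Baseline was above ULN. It groups patients by size of elevation and reports the outcome "with the following categories of normalization: never normalized, normalized after permanent discontinuation of study drug". It adds: "Note that a patient will be counted only under the maximum elevation category". It names no residual category and no denominator.

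Three other protocol sections bear on what happens to a patient with an abnormal test:

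- Section 10.3.1: "All IMP discontinuation should initially be considered as temporary unless permanent discontinuation is mandated by the protocol".
- Section 10.4.6, whose list of abnormalities includes an increase in ALT, says that where the laboratory guidance requires IMP to be stopped, "temporary discontinuation should be considered unless otherwise specified".
- Section 10.3.3: "Any abnormal laboratory value or ECG parameter will be immediately rechecked for confirmation before making a decision of permanent discontinuation of the IMP".

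SAP 1.1 says that "this plan takes precedence where there are differences between the two documents". For laboratory data, SAP 2.4.5.2 says: "Summary statistics of all laboratory variables (number, mean, standard deviation, median, first quartile, third quartile, minimum, and maximum) will be calculated". Under drug-induced liver injury, SAP 2.4.5.1 says: "These events will be presented in the same manner as EOSI". Neither SAP section mentions normalization. SAP Appendix D, the list of key changes, does not mention the table.

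**The concern.** A patient with an elevated liver test can end in one of several states: the test never recovers, it recovers with IMP continued, it recovers around a temporary interruption, it recovers after IMP is stopped for good, or it is never repeated. The table has rows for the first and the fourth only. Its single recovery row belongs to the disposition that section 10.3 calls a last resort.

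The protocol says these tests are used to assess possible drug-induced liver toxicity. Whether a raised value settles with the drug continued, interrupted or permanently withdrawn is part of that assessment, and this table cannot show the first two. With no stated denominator, two programmers could also produce different percentages from the same data.

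**Working it through.** The plan gives no figure to reproduce here, so the check has three parts.

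**1. Are the categories exhaustive?** Set each possible course against the two rows.

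| Course after an elevation | Row in the table | Where the protocol allows for it |
|---|---|---|
| Never recovers | Yes | 11.4.3.5 |
| Recovers with IMP continued | None | 10.3.3 requires a recheck before a permanent stop, so a value can recover on IMP |
| Recovers during or after a temporary stop | None | 10.3.1 and 10.4.6 |
| Recovers after a permanent stop | Yes | 11.4.3.5 |
| No later test | None | Not addressed |

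The list is not exhaustive.

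**2. What would the table show?** The documents give no split of these outcomes, so the splits below are assumptions for illustration. Take 20 patients with an elevation: N never recover, A recover on IMP, T recover around a temporary stop, P recover after a permanent stop. The true never-normalized share is N/20. Three handling rules are possible for the A + T patients with no row:

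- (a) all elevated patients form the denominator: N/20
- (b) unplaced patients are dropped: N/(N + P)
- (c) unplaced patients are counted as never normalized: (N + A + T)/20

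| N / A / T / P | True | (a) | (b) | (c) | Patients with no row |
|---|---|---|---|---|---|
| 4 / 8 / 5 / 3 | 20% | 4/20 = 20% | 4/7 = 57% | 17/20 = 85% | 13 |
| 4 / 2 / 1 / 13 | 20% | 4/20 = 20% | 4/17 = 23.5% | 7/20 = 35% | 3 |
| 4 / 0 / 0 / 16 | 20% | 4/20 = 20% | 4/20 = 20% | 4/20 = 20% | 0 |

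Under rule (a) the never-normalized share is right, but recovery is under-reported. In the first split, 16/20 = 80% recovered, the table shows 3/20 = 15% as recovered, and 13/20 = 65% appear nowhere. In the last split nothing is lost. The never-normalized share is therefore distorted only under (b) or (c), and only when such recoveries occur.

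**3. Bilirubin.** E 31 excludes total bilirubin above 1.7 x ULN (with an exception for Gilbert's syndrome). The lowest bilirubin threshold in the table is 1.5 x ULN. A patient who enters at 1.6 x ULN and stays there is above the threshold and, at the same visit, at Baseline. Because a return to Baseline counts as normalization when Baseline exceeds ULN, this patient can be read as elevated and normalized at once while still on drug, again with no row.

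**The case against.** A reader might infer that the table overstates non-recovery. The documents do not support that as a finding. The label for non-recovery excludes, by its plain meaning, anyone whose test recovered by whatever route. The natural denominator is everyone in the elevation category, and with it the non-recovery share is correct. Overstatement needs a handling rule that the protocol does not contain. This part of the objection stands.

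It is also fair to say that the protocol does not show the omitted outcomes to be common. No frequencies are given. Stops are only initially temporary and may later be made permanent, and restarting requires the Investigator to judge that IMP was unlikely to be responsible. Some recoveries would therefore fall in the existing row. That limits what can be said about size. It does not supply the missing rows.

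The assessment of liver injury does not rest on this table alone. Section 6.4.5 sets up a treatment-blinded committee for potential cases, and 11.4.3.5 also plans flagged listings, abnormality tables by Baseline status and by exposure, and a plot of peak ALT against peak bilirubin. This lowers the stakes. None of these is described as tabulating recovery by treatment status.

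Finally, the SAP takes precedence and has no such table, so it may not be produced at all. But SAP 1.1 introduces the document as a plan for efficacy analyses, its safety sections are brief, and Appendix D lists only key changes. Its silence neither keeps nor withdraws the table.

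On bilirubin, one can argue that a return to Baseline presupposes a prior rise. That is a reasonable reading, but the text does not say so.

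**Conclusion.** The point holds as a modest specification defect. The two categories do not cover the outcomes that the protocol itself provides for, and no denominator is stated. Followed as written, the table under-reports recovery, and its rows fall short of the number of patients with an elevation whenever anyone recovers on IMP or around a temporary stop.

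The size cannot be derived from the documents. The range of 20% to 85% in the first illustrative split shows only what an unstated handling rule could do under an assumed mix of outcomes; it is not an estimate for this trial. If no patient recovers on IMP or around a temporary stop, those omissions cause no distortion.

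Whether the table is still planned is unclear. It is a descriptive safety display, with no hypothesis test, power figure or type I error attached.

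**What to change.** Replace the two categories with an exhaustive set:

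- never normalized
- normalized while IMP continued
- normalized during or after temporary discontinuation
- normalized after permanent discontinuation
- no follow-up test available

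State that the denominator is all patients in the given elevation category, so that the rows add up to it. For bilirubin, flag separately values above 1.5 x ULN that do not exceed the patient's own Baseline. Add one sentence to the SAP saying whether this protocol table is kept. If it is dropped, record that in Appendix D.

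The cost is a few sentences and three extra rows. Section 10.3.1 already has the start and end dates of temporary stops recorded in the e-CRF, and SAP 2.5.1 takes the last-dose date from the IMP administration page. No new data are needed and patient management does not change.
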